## **Risk and Benefits**

### **Potential risks**

We believe there is low risk associated with this study. This study does not involve any medical procedures and we believe the probability of experiencing social harms to be low. That being said, we have carefully considered all possible risks to participants (regardless of their probability) in the various phases of the study. Potential risks to participants in this study include: 1) COVID-19 related risks during in-person study activities, 2) emotional discomfort and distress resulting from the topics covered in the IDIs or during assessments for the pilot study, 3) emotional discomfort or distress when reading content on the app, 4) unintended disclosure, 5) violations of privacy and confidentiality concerns, and 6) risks of coercion. We believe that the steps described below will minimize or prevent these potential risks.

### **Protection against risks**

**COVID-19 related risks.** COVID-19 related risks may be possible during in-person study activities. To reduce the spread of COVID-19, and to limit the exposure among participants and staff, we will implement all UCT-approved COVID-19 guidelines and recommendations to keep our participants and staff safe. Our staff will continue to follow all active FHS SOPs before, during, and after all study visits.

**Emotional discomfort and distress.** The topics covered in the IDIs or during assessments for the pilot study will involve sensitive topics (e.g., challenges with adherence, stigma) that may lead to distress and emotional reactions. To protect against emotional distress, each interview will begin with an explanation that participants are free to refuse to answer any question and may terminate the interview at any time. Interviewers will be trained to identify and respond to signs of discomfort and distress.

Participants may also experience *emotional discomfort or distress* when reading content on the app. We will strive to create a safe and comfortable app environment for all study participants. However, it is possible that participants in the intervention arm may experience emotional discomfort or distress due to things other participants post through the app's forums. We will provide participants with information to allow them to contact the study team at any time if they experience emotional distress related to participation in the study. We will also include "community guidelines" as part of the intervention app's on-boarding process. This information will also be included within the app. During the formative phase of this research, we will review these guidelines to ensure they are comprehensive given the regular evolution of online environments and social media tools. The guidelines will continue to include language around non-discrimination, non-offensive language, openness and confidentiality.

During the pilot study, study staff, including Peer Mentors (who will be hired to engage with participants within the app) will review and help monitor forum posts. Study staff will monitor posts made during business hours with posts made outside of business hours reviewed in the morning of the next business

day. If a participant posts something that could be considered in breach of the guidelines, study staff will remove the post and contact the participant to notify them and explain why the post was removed. Our protocol describes additional action steps should a participant accumulate three violations of this nature. Study staff will also monitor posts for content that indicates a need to implement the SOP for Various Scenarios, including concerns about harm to the participant or others.

*Unintended disclosure.* Unintended disclosure is also a potential risk. Study staff will be trained (or re-trained) on confidentiality standards and proper interviewing techniques to minimize this risk. Participant names will not be included in any data collection instruments or intervention forum posts. The only numbers used to label and identify data from the participant will be the Study ID or their username (app handle) for the intervention. Questionnaires and audio files will be linked using the Study ID and the interview date. We also have extensive data procedures already in place to ensure security of the data and information provided by participants. Data will not be released to non-study staff at any time. All electronic data sharing between sites will be done only on the secure server (e.g., via Duke Box.com).

*Privacy and confidentiality concerns.* Participants may have privacy and confidentiality concerns. Participants will be reminded to consider their surroundings and the privacy of their device before engaging with the intervention app. No communication between study staff and participants will include sensitive information about HIV or anything that could reveal their participation in a study. To protect their privacy, participants will be required to enter a PIN to gain access to the app if it has been 5 minutes since the app was open on their device, or 15 minutes if the app was open but inactive as a fail-safe to avoid unintended disclosure. Participants will also be encouraged to interact with the study application when in private. Participants in focus group discussions will be asked to respect confidentiality and not share the identities of other participants or content shared in the discussions. Finally, participants will be notified of these risks in the consent process.

*Risks of coercion.* There may also be risks of coercion. We are aware of the ethical considerations in providing compensation to people living in impoverished conditions because providing compensation may unintentionally coerce participation in research. Thus, we will limit the compensation amount to no more than R250 per study visit. Additionally, participants will be reminded that the study participation is voluntary and that refusing to participate in the study or withdrawing from the study is an option at any time.

### **Potential Benefits**

There are no direct benefits to adolescents who participate in this study. Participants may benefit from knowing that the information learned from this study will help to improve the situation of youth like themselves. If the pilot RCT is successful there are potential social benefits that can be gained from the study. The proposed research may identify new insights into how to best support adolescents living with HIV using mobile technology. The risks to participants are reasonable in relation to the anticipated benefits of the research.

### **Confidentiality**

Confidentiality is of critical importance, and we will take precautions to protect against the possibility of a confidentiality breach. We will conduct study visits in a private area so that participants can speak without being overheard. Minimal identifying information will be collected during the IDIs. When the digitally recorded interview is transcribed, only nick names or fictional names will be used. Study documents will only be identified only by a study ID number, not by name. The research team will maintain a separate list that links the study ID number with the personally identifying information. This list will be kept in a locked filing cabinet at UCT and/or in password protected files on password protected computers and secure servers. Other paper study documents (e.g., written informed consent forms and hard copies of data) will be kept in a locked filing cabinet at UCT. All electronic data collected in this study will be stored on a secure and confidential server housed at the University of Cape Town, Duke University, and Florida State University. Participants' names will never appear in any report resulting from the project.

Any content that participants share on the app will only appear with their username. To protect their privacy, we will encourage participants to choose a unique username that is different from their real name, email address, and their social media accounts. We will strongly discourage participants from sharing personal information in the app that could reveal their identity. If a participant chooses to share identifiable information about themselves in the app, it may result in the breach of their confidentiality to other participants. We reserve the right to remove it from the app if it violates our app guidelines. Any study-related messages that are sent to participants will not disclose the fact that they are in a research study. All messages will be free of any identifying information and will not have any personal health information. To further ensure participant privacy, we will encourage participants to change the settings on their phone to keep the body of text messages from appearing on the main screen when they receive a message.

In instances where something a participant says or does indicates potential harm to the participant or

others, we are legally required to report the concern. We have created an SOP for various scenarios (see Research Protocol appendix) that outlines the conditions and procedures for reporting in accordance with the South Africa's Children's Act.

Thus, while we acknowledge that a breach of confidentiality is possible, the likelihood is very low.

### **Compensation, Transportation, and Refreshments**

We will provide participants R250 per study activity for time and travel. This is consistent with the compensation provided to participants in the larger/main NASA study. Additionally, participants who participate in the second set of IDIs for beta-testing the app will be given smartphone data to support their use of the app during that period. Participants in the pilot study will be given smartphone data to support their use of the app for 6 months.

We will arrange for a registered and reliable transport company to collect the participants (and their parent/ legal guardian / caregiver) in their area of residence and bring them to the Department of Psychiatry and Mental Health, University of Cape Town for the assessments. Having participants picked up and dropped off for their study visits ensures that they arrive on time and at the correct location. Providing reliable transport for participants to the study sites also significantly decreases the rate of no-shows and losses to follow-up. We will also provide participants with light refreshments after their participation in these study activities.

### **Informed consent**

Prior to participating in this study, participants/caregivers will provide informed consent (and assent, if applicable). All adolescents under 18 years of age will be required to have parental/ legal guardian / caregiver consent. For these adolescents, we will seek parental/ legal guardian/ caregiver consent and the adolescent will be asked to provide assent to participate. As is done in the larger/main NASA study, informed consent forms will be provided in English and the study staff will be bilingual and able to ensure full comprehension. A study staff member will describe the study in detail to the participants, allow them ample time to read the consent form thoroughly (or have it read to them) and ask questions, and ensure that they understand the study purpose, procedures involved, and potential risks. Participants will be told that their decision to participate will not affect their current or future health care at the HIV clinic. Participants will have the opportunity to ask questions regarding the consent. Verification of comprehension of the consent form will be accomplished by asking participants to recall central points in the consent process, including the purpose of the study, procedures involved, and potential risks. This verification will also provide an opportunity to clarify any points of confusion. Participants (or their parent/ legal guardian/ caregiver, if applicable) will sign two copies of the informed consent form, one for the study records and one to take for their personal documentation.

## Statistical Analysis Plan

The study will enroll 50 adolescents and young adults with HIV into the study (25 males and 25 females based on self-reported sex assigned at birth). The study's sample size ( $n = 50$ ) was selected to be large enough to reasonably evaluate the feasibility and acceptability of MASi while balancing budgetary constraints.

Descriptive summaries will be computed for all study outcomes with continuous variables summarized with means and standard deviations (or medians with interquartile range in the case of skewed distribution) and categorical variables summarized with counts and proportions. Outcomes will be summarized, stratified by treatment group, at each available study time point.

As a pilot study with a primary focus on feasibility and acceptability, the examination of MASi's preliminary efficacy will be exploratory. To explore MASi's preliminary efficacy on ART adherence and social support at 3- and 6-months, we will use linear mixed models to compare outcomes among participants randomized to MASi compared vs. the information-only control at each time point. Log transformed outcomes and alternative modeling approaches such as Poisson and negative binomial will be considered in the event that assumptions for the linear model are violated. All models will include a fixed effect for sex assigned at birth (stratification variable) and a random intercept term to account for correlation in the response due to repeated measures within study participants over time. A random slope for participant will also be considered, as will the covariance structure of the errors (e.g., exchangeable, autoregressive). Distribution of residuals will be examined to confirm that modeling assumptions are met. Because sample size is small (this study is not powered to detect clinically meaningful effect sizes) and the regression analyses are exploratory in nature, inference will focus on the size and direction of the total treatment effects rather than statistical significance.

Additional exploratory analyses will examine MASi's effects over time on HIV/AIDS knowledge and stigma using methods similar to those employed for adherence and social support outcomes. We will also conduct descriptive analyses examining trends and patterns in user engagement with various components of the MASi interface over time.

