- Knows HIV status (Screened AYA who do not know their HIV status will receive information on free voluntary HIV counseling and testing services)
- Living with HIV
- Has been prescribed medication to treat HIV
- Not attending school for learners with special needs (e.g., School of Skills)
- Has not repeated a grade in school more than once
- Have a smartphone that can download apps
- Feels comfortable using an app with content in English
- No plan to move outside of Cape Town in the next six months

- Have not previously participated in the MASi app testing phase of our study

Participants who meet these criteria will be invited for an in-person appointment. After completing the informed consent/assent process (including consent from an adult, if applicable), we will confirm the final eligibility criteria:

- Able to successfully install the MASi app on their smartphone

Eligible participants will complete a baseline assessment, which will be an interviewer-administered survey with data entered electronically by the interviewer using REDCap data collection software. Paper surveys will be available in the event online data entry is not possible. For survey questions with a higher potential for social desirability bias (e.g., sexual behavior and study feedback), we may offer participants the opportunity to self-enter data into REDCap.

Following the baseline assessment, the interviewer will use REDCap's randomization tool to assign participants to condition. Using this process, participants will be randomized to the intervention or control condition (1:1), with randomization stratified by gender. The intervention condition will include all features of *MASi* while the control condition will be an information-only version of *MASi* which will include the Resources feature and homepage. Study participants will be asked to engage with the app for 6 months. All participants will receive 1G in monthly cellphone data packages for 6 months; research staff will touch base with participants each month to ensure the participant still has access to a working device before sending data.

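### Does n = 50 overstate the evidence on MASi, when only about 25 receive the full app and people who cannot install it are excluded before randomization?

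*Combined protocol and SAP*

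**What the plan says.** The sample-size statement in the Statistical Analysis Plan is verbal. "The study will enroll 50 adolescents and young adults with HIV into the study", and that number "was selected to be large enough to reasonably evaluate the feasibility and acceptability of MASi", weighed against the budget. No target precision, success threshold, power or dropout rate goes with it. The same section makes feasibility and acceptability the primary focus, treats efficacy as exploratory, and says the study is not powered for efficacy.

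The design is set out under Aim 3: "participants will be randomized to the intervention or control condition (1:1), with randomization stratified by gender". The intervention arm has all features of the app, while "the control condition will be an information-only version of *MASi* which will include the Resources feature and homepage". Both arms are asked to use their version for 6 months, receive monthly data, and are assessed at 3 and 6 months.

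The last eligibility criterion, confirmed in person after consent and before baseline and randomization, is "Able to successfully install the MASi app on their smartphone". On reporting, the Statistical Analysis Plan says: "Outcomes will be summarized, stratified by treatment group, at each available study time point".

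**The concern.** Two features seem to flatter the primary question.

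First, the sample-size sentence sets the whole 50 against the evaluation of MASi. Control participants never see the forums, Med Tracker, Ask an Expert, activities or gamification, so they cannot rate or use them. The Statistical Analysis Plan itself contrasts people randomized to MASi with an information-only control. A reader could take the acceptability and engagement figures to be firmer than 25 people can make them, and no confidence intervals are promised for those summaries.

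Second, being unable to install a smartphone intervention is arguably a feasibility failure. It is handled as ineligibility, before randomization, so summaries by treatment group cannot contain it. If such failures were common, a feasibility percentage among randomized participants would describe only those past the first hurdle. That would matter for any claim that the app could be scaled up in this setting.

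**Working it through.** **The plan's own figure.** n = 50 cannot be reproduced, because the documents give no inputs for it. The one check available is the split: 50 at 1:1 is 25 per arm. With 25 in each randomization stratum, an odd number, each stratum divides 12/13, so arms of roughly 24 to 26.

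**Precision for a proportion.** The 95% Wilson interval, with z = 1.96, has

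- centre = (p + z²/2n) / (1 + z²/n)
- half-width = z √(p(1−p)/n + z²/4n²) / (1 + z²/n)

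For p = 0.8 and n = 25: centre = (0.8 + 0.0768)/1.1537 = 0.760; half-width = 1.96 × √(0.0064 + 0.00154)/1.1537 = 0.151; interval 0.609 to 0.911. The documents give no expected rate, so 80% and 60% are assumed for illustration.

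| Observed rate (assumed) | n = 50 | n = 25 |
|---|---|---|
| 80% | 67% to 89% | 61% to 91% |
| 60% | 46% to 72% | 41% to 77% |

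Half-widths go from about 11–13 to about 15–18 percentage points. In the simple large-sample formula the ratio is √(50/25) = 1.41. For a mean score the 95% half-width is 0.28 SD with 50 and 0.41 SD with 25.

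**Which measures this touches.** Full-app acceptability, usability and engagement rest on about 25. Recruitment, retention, assessment completion and use of the Resources feature can draw on all 50, since controls also install and use a version of the app.

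**Install failures.** Let f be the share of consented, otherwise eligible people who cannot install. The documents give no f; 0% to 20% is assumed. Enrolling 50 needs 50/(1−f) consented. With 45 of 50 retained (90%, also assumed), the same 45 over all consented is 0.90 × (1−f).

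| f (assumed) | Consented needed | 45 retained / consented |
|---|---|---|
| 0% | 50 | 90% |
| 5% | 53 | 86% |
| 10% | 56 | 81% |
| 20% | 63 | 72% |

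The last column is not a corrected retention rate. It is enrolment yield multiplied by retention. A person who was never randomized is not a retention failure, so 90% among randomized and 72% of consented can both be true and answer different questions.

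**Scope of the by-arm sentence.** It governs study outcomes at study time points. Screening, consent and installation counts precede assignment and are not outcomes by arm; nothing in the documents plans or rules out reporting them.

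**The case for a change.** The strongest case for a change is that feasibility and acceptability are the primary focus, yet the plan gives them neither denominators nor precision. It would cost only a few lines to state 25 for the full-app measures, 50 for recruitment and retention, and a funnel from consent to completion. Phone screening already requires a smartphone that can download apps, so a later install failure is failure of this app in a willing, otherwise eligible person. That is real feasibility information.

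Much of this is fair. About 25 people do carry the full-app findings, and by-arm summaries cannot show install failures. A good report would make both visible.

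The stronger charges do not stand. The plan does not credit MASi figures with twice their people: it states no interval or denominator, and reporting by arm will put those figures on about 25. A result that is too favourable requires install failures to occur and installability to belong to the feasibility measure; the documents establish neither. Aim 2 also puts the app on participants' phones and collects technical difficulties before the pilot. The check applies before randomization to everyone, so it does not bias the comparison between arms. Nothing in the Statistical Analysis Plan limits engagement summaries to users, so counting non-users as zero would correct no stated rule.

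**Conclusion.** No change to the plan is needed. The loss of precision for full-app measures is real: for an observed 80%, a half-width of about 15 points with 25 people against about 11 with 50. But it follows directly from 1:1 allocation and contradicts no claim in the plan. For a pilot whose size was openly a compromise with budget, that is a fair trade-off. The effect of install failures cannot be sized from the documents. It is zero if nobody fails, and the 86%, 81% and 72% figures rest on assumed failure rates and on replacing retention with a different measure.

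What remains is unwritten reporting detail: the denominator for each measure, an interval beside it, and the number of consented people who could not install the app. The by-arm layout makes the first evident, and the other two can be computed when the pilot is reported, provided the eligibility-visit result is kept. This conclusion assumes that full-app figures are reported for the intervention arm alone, as the plan indicates, and that retention is described as retention among those randomized.

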Participants will complete follow-up assessments as well as 3- and 6-months follow-up. Assessments will take approximately 60 minutes and will be conducted in a private room so that participants can speak without being overheard. Phone assessments may be conducted in the event it is not possible to conduct in-person data collection. Assessments will include questions about assessing demographics, HIV-related knowledge, social support, loneliness, resilience, anxiety, depression, stigma, disclosure concerns, disclosure intentions, treatment adherence, sexual activity, perceived usability of *MASI*, and participant feedback about the study overall.

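### Does the SAP's by-arm, by-time-point summary describe feasibility and acceptability only in the participants who stay?

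*Combined protocol and SAP*

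**What the plan says.** The Statistical Analysis Plan sets the priority: "As a pilot study with a primary focus on feasibility and acceptability", with efficacy exploratory. All outcomes get means and standard deviations, medians, or counts and proportions, under one layout rule: "Outcomes will be summarized, stratified by treatment group, at each available study time point". A separate paragraph adds "descriptive analyses examining trends and patterns in user engagement with various components of the MASi interface over time". The section does not name the feasibility and acceptability measures, state a denominator, or mention a participant flow.

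The Aim 3 text of the protocol supplies the context. The assessment topics end with perceived usability of the app "and participant feedback about the study overall". For missed visits there is a fallback: "Phone assessments may be conducted in the event it is not possible to conduct in-person data collection". After consent, and before baseline and randomisation, one last eligibility criterion is confirmed: "Able to successfully install the MASi app on their smartphone". During the six months, "research staff will touch base with participants each month to ensure the participant still has access to a working device before sending data". The section on compensation and transportation says that arranged transport "significantly decreases the rate of no-shows and losses to follow-up".

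**The concern.** In a pilot of an app, those who drop out, lose their phone or cannot install the app carry much of the information on feasibility. Three features suggest the plan might lose them.

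- Usability and feedback are survey answers, so a proportion by arm at 3 or 6 months will naturally be computed among those who answered. If people who dislike the app are less often assessed, that proportion is too favourable.
- A consenter who fails installation is never randomised and cannot appear in any summary by treatment group.
- The engagement analysis does not say whether a participant without a working device counts as zero use or drops out of the average.

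Meanwhile the exploratory outcomes, adherence and social support, get mixed models that use partial follow-up. The primary focus appears to have the weaker plan. What would be at stake is the pilot's main message: four in five participants finding the app acceptable could be a statement about completers only.

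**Working it through.** **Inputs.** From the documents: 50 enrolled, allocated 1:1, so about 25 per arm; assessments at 3 and 6 months; installation checked after consent and before randomisation. The 50 is 25 males plus 25 females, which adds up; it was set by judgement and budget, so no formula can reproduce it. Not in the documents, and so assumed: the number assessed, an 80% favourable share among them, the rate of device loss and the rate of installation failure.

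**Acceptability.** With *k* of 25 assessed and *s* favourable, the share among all randomised lies between *s*/25 and (*s* + 25 − *k*)/25.

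| Assessed | Observed (exact 95% CI) | Lowest over 25 | Highest over 25 |
|---|---|---|---|
| 25 | 20/25 = 80% (59 to 93) | 20/25 = 80% | 20/25 = 80% |
| 20 | 16/20 = 80% (56 to 94) | 16/25 = 64% | 21/25 = 84% |
| 15 | 12/15 = 80% (52 to 96) | 12/25 = 48% | 22/25 = 88% |

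With observed share *p* and missing share *q*, the figure can fall by *pq* or rise by (1 − *p*)*q*, a ratio of *p*/(1 − *p*). That is 4:1 at 80%, 1.5:1 at 60% and 1:1 at 50%, so the lopsidedness comes from the assumed 80%. The lower bound needs every unassessed person to be unfavourable. With five missing, even that extreme (64%) lies inside the sampling interval for 16/20; with ten missing, 48% falls just below the interval for 12/15. If usability is a scale score, the SAP calls for means or medians and these proportions do not apply.

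**Engagement.** If use per device holder is constant and a share *d* lose the device, the mean over all randomised is (1 − *d*) times the holders' mean: 100%, 80% or 60% of its start for *d* = 0, 0.20 or 0.40. The two presentations differ, but the SAP does not choose the one restricted to holders.

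**Installation.** If 0, 5, 10 or 20% of consenters fail, enrolling 50 takes 50, 53, 56 or 63 consenters, leaving 0, 3, 6 or 13 people with no arm. Installed over consented is 50/50 = 100%, 50/53 = 94%, 50/56 = 89% or 50/63 = 79%. These people never used the app, so leaving them out of an arm-level summary cannot bias acceptability among users. They are a feasibility count that belongs in the participant flow.

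**Reading the sentence.** *Available* modifies the time point: an outcome is summarised at the visits where it is collected. Counts and proportions can be given over all randomised with a row for missing answers. Someone lost after month 3 still counts at month 3. App use is tracked by the app itself, so describing it needs no visit.

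**The case for a change.** The strongest case for a change is that silence has a default. With no stated denominator, software gives the proportion among responders, and that would be the headline for the pilot's primary focus. The investigators plainly regard losses as possible, since they arrange transport and check devices every month. Phone assessment is permitted but not required, and is not described as a way to reach people who disengage. A participant flow would show the losses but leave the acceptability proportion unchanged. Stating the denominators would cost only some wording, a log of installation failures, and keeping the device-check results.

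Part of this stands. The SAP does not name its measures or denominators, and writing them down would be good practice. The rest is weaker. The mixed models also use only observed outcomes, and the SAP gives them no missing-data rule either. No loss rate is stated, and several features work to keep losses low: payment of R250 per activity, transport, monthly contact with data, and exclusion of anyone planning to leave Cape Town. The protocol also refers to an appendix and further procedures outside this text, so firm claims of absence are unsafe.

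The one proposal that would alter a reported result is to make all randomised the denominator and count the unassessed as not favourable. A missed visit is not a verdict on the app. That rule merges retention, a feasibility outcome, with acceptability, and it can only lower the figure. It is a choice with a cost, not a correction.

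**Conclusion.** The concern does not call for a change. The SAP leaves denominators, measures and participant flow unstated, but it states no rule that gives a wrong result. An analyst following it would ordinarily put the numbers randomised and assessed beside each summary and report retention, screening, consent, installation and randomisation counts. A reader could then derive the bounds.

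The possible gap runs from nothing, with full follow-up, to 16 points down or 4 up with 20 of 25 assessed, and 32 down or 8 up with 15 of 25. All of this rests on assumed attrition, an assumed 80% favourable share and, at the extremes, unanimous opinion among the unassessed. The SAP describes these outcomes without a pass mark, so no stated decision turns on the difference. Naming the items, giving exact intervals or showing the range as a sensitivity display would be reasonable reporting additions, but they would not alter the design or its conclusions.
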